The ED study will also include provider participants who will be asked to complete a demographics survey and a brief interview about each of their index study patients after their intervention with the patient is complete. The brief interview will be administered in-person and assess the provider's feeling of preparedness for the assessment, the patient's degree of distress at the time of encounter, helpfulness of Jaspr's clinical support tool in discharge disposition determination, and risk assessment (if applicable).

ED study primary outcome variables include: suicidality (death by suicide, suicide attempts, suicidal ideation), ED/hospital admissions, discharge disposition, use of restraints while in ED (chemical, physical), intensity ratings of acute distress, self-efficacy in coping with distress, use of imminent distress intervention and coping skills, and helpfulness of their ED encounter. Jaspr condition-specific outcomes will be examined and reported descriptively. These include tools accessed during and after the ED visit, perceived usefulness and satisfaction of Jaspr brief intervention components, and usage of provider/patient apps and their features.

Telehealth study primary outcome variables include: suicidality (death by suicide, suicide attempts, suicidal ideation); Crisis-related healthcare utilization (ED visits, psychiatric hospitalization, calls to crisis line; crisis calls to therapist; Outpatient Satisfaction; Use of evidence-based interventions to reduce suicide risk (safety planning, lethal means management, behavioral skills). Secondary outcomes include: Reasons for living; Psychological distress (depression, anxiety, stress); Cognitions associated with suicide risk (hope, optimism, pessimism).

The primary hypotheses include:

1. Jaspr patients will report significantly greater decrease in suicidality and ED/hospital admissions than CAU patients from the initial session to follow-up assessments.
2. Jaspr patients will report significantly greater increases in self-efficacy in coping with acute distress, use of acute crisis tolerance skills, and perceived helpfulness of the care they receive compared to CAU patients.
3. Jaspr patients will report high levels of satisfaction with Jaspr.

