#### ED Study

**Patient Participants:** Because the patient's medical treatment is of foremost importance and to accommodate the fluid, unpredictable environments in the ED and to work within their usual flow, the researchers will pause all research procedures whenever necessary to allow for the patient's medical care and resume should there be additional periods of waiting. Once enrollment is complete (i.e., consent is obtained), the researchers will request a release of information from the participant for information we would like to gather from a member of their care team after the patient's discharge. Specifically, we are interested in collecting data about the patient's length of stay, if physical or chemical restraints were used and if so for how long, their final discharge disposition (e.g., if the patient was admitted to inpatient, residential, or substance abuse treatment or discharged to home), and if the patient was admitted whether it was involuntary or voluntary. This data will be obtained orally by speaking with a member of the patient's care team; medical records will not be accessed by the researchers. Permission (or not) for this release of information will not impact the patient's participation in the study (i.e., if they decline to provide permission for this release, they may still participate in the study). If the patient agrees to provide permission for the researcher to collect this information, they will be asked to sign a release of information form.

The researcher will then conduct the baseline assessment and the researcher will randomize the patient to condition while the participant is completing baseline measures. The researcher will inform the patient of the condition they have

been assigned after they have completed the baseline assessment.

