***Analysis Strategy.*** We will use SPSS Version 23. For patient data, we will use Hierarchical Linear Modeling (HLM). HLM provides greater flexibility in that it can analyze a variety of commonly encountered outcome distributions (e.g., continuous, binary count), test the fit of different covariance matrix assumptions; and include participants who are missing data at some time points. We will account for nesting of patients under providers by including providers as a random effect; we will account for nesting within sites by including dummy coded fixed effects predictors representing site in all analyses. For each outcome, we will specify the correct distribution and compare fit indices to identify the covariance matrix best fitting the data. Many hypotheses relate to change over time, and so the multiple time-points will be treated as nested within the individual. Also, we will treat the intervention conditions (Jaspr and JAH) and time as categorical, dummy-coded predictors; the control conditions and baseline scores will serve as the reference category. The parameter of interest will be the Time X Condition interaction, and the Type III statistic will serve as an omnibus test of whether the two conditions differed in change over time. Regression coefficients will indicate at which follow up time points the conditions showed differential change from baseline. For patient satisfaction as well as the secondary hypotheses concerning medical providers ratings of helpfulness, we will compute descriptive statistics and consider ratings to be favorable using the *a priori* established criteria that 80% or more respondents rate program components as favorable or highly favorable. For the remaining secondary hypotheses, which are based on provider data about patients from both conditions at one time point, we will compute between-condition means. Since it is possible that not all providers will be able to provide data given time constraints inherent in their job, we may not have the statistical power to conduct probability tests. Hence, we will examine the data descriptively to provide preliminary information about efficacy and compute effect sizes to inform future research.

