***Statistical Power Considerations.*** For Hypotheses 1 and 2, we conducted power analyses focused on the ability to detect statistical significance on the key parameter of interest, the Time X Condition interaction. Power analyses assumed equal size groups,  $p \leq .05$ , power of .80, and two-tailed tests. Using GPower's utility for the General Linear Model, we found that a total sample size of 24 patients would allow detection a medium effect ( $f > = 25$ ). However, this assumes no design effects (DE) that occur due to the nesting of patients under physicians. In the likely event that design effects exist, a sample of 72 participants will allow sufficient power to detect a medium effect with DEs as great as 3.0). Adjusting this number for possible 20% attrition, we would need to enroll at least 90 patients, but will strive to include 120 patients total in this research to ensure we have sufficient statistical power for all outcome variables.

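### The assurance of adequate power for every outcome rests on one repeated-measures calculation that does not cover restraint use, discharge disposition or event outcomes

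*Combined protocol and SAP*

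**What the plan says.** The power paragraph in section 5.B states that it concerns Hypotheses 1 and 2 and that the parameter powered is the Time by Condition interaction, two-sided at .05 with 80% power and equal arms. From G*Power's General Linear Model routine it reports that "a total sample size of 24 patients would allow detection a medium effect". It then allows for nesting of patients under physicians: "a sample of 72 participants will allow sufficient power to detect a medium effect with DEs as great as 3.0". Adding 20% attrition gives a floor of 90, and the plan will strive for "120 patients total in this research to ensure we have sufficient statistical power for all outcome variables". The step from 90 to 120 has no derivation of its own.

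The outcomes are set out in section 3: "ED study primary outcome variables include: suicidality (death by suicide, suicide attempts, suicidal ideation), ED/hospital admissions, discharge disposition, use of restraints while in ED", followed by distress, self-efficacy, skill use and helpfulness ratings. Hypothesis 1 states that "Jaspr patients will report significantly greater decrease in suicidality and ED/hospital admissions than CAU patients". Hypothesis 2 concerns self-efficacy, skill use and perceived helpfulness. Neither names restraint use or discharge disposition.

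Section 5.A (ED Study, Patient Participants) describes a report obtained from the care team after the patient's discharge, covering length of stay, "if physical or chemical restraints were used and if so for how long, their final discharge disposition" and whether any admission was voluntary. It depends on a signed release: "if they decline to provide permission for this release, they may still participate in the study".

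For secondary provider ratings, the Analysis Strategy in section 5.B says "we may not have the statistical power to conduct probability tests" and plans to describe those data.

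**The concern.** One calculation, for one type of parameter, is followed by an assurance about every outcome. An interaction with time needs repeated measurement, and an f from a normal-theory linear model needs a roughly continuous outcome. Several ED primary outcomes lack one or both features. The figure of 24 is as low as it is because each patient contributes several correlated measurements, and an outcome recorded once does not have that advantage.

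What is at stake is interpretation. This paragraph is the only justification for the floor of 90 and the target of 120. If the trial finds no significant difference in attempts, admissions, restraint use or disposition, a reader could cite the paragraph to call that an adequately powered null result. Nothing in the plan would support that reading.

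**Working it through.** **1. The plan's own figure.** Inputs from section 5.B: alpha .05 two-sided, power .80, two equal arms, f = .25. The effect size prints as 25; I read it as .25 because it is called medium and because that value reproduces 24. The number of visits, their correlation and sphericity are not stated. I infer m = 4 visits, correlation rho = .5 and sphericity.

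- Noncentrality: lambda = f² × N × m / (1 − rho) = .0625 × 24 × 4 / .5 = 12.0
- Degrees of freedom: m − 1 = 3 and (N − 2)(m − 1) = 66
- Power: 81.6%. With N = 22 it is 77.5%, so 24 is the smallest even total.
- Design effect: 24 × 3.0 = 72. Attrition: 72 / 0.8 = 90.

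The chain holds. The inferred inputs are not unique: 3 visits with correlation .6, or 5 visits with .45, also give 24.

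**2. Which outcomes the calculation reaches.**

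| Outcome | Named in Hypothesis 1 or 2 | Measured repeatedly from baseline | Rate or SD stated |
|---|---|---|---|
| Discharge disposition, restraint use | No | No: one report after discharge, only with a release | No |
| Deaths | Yes (suicidality) | No: no baseline from which to change | No |
| Attempts, ED/hospital admissions | Yes | Followed over time, but events or counts | No |
| Ideation, self-efficacy | Yes | Treated as continuous repeated measures | Covered through f = .25 |

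**3. Scale for a continuous outcome recorded once.** Same f, alpha and power, no design effect. Two-group F test with lambda = N × f² and degrees of freedom 1 and N − 2.

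- N = 120: lambda = 120 × .0625 = 7.5, power 77.5%
- N = 126: lambda = 7.875, power 79.5%
- N = 128: lambda = 8.0, power 80.1%

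So 128 analysed are needed, against a target of 120 enrolled.

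**4. Scale for yes/no outcomes.** The documents give no rates, so these are assumptions. There is no design effect, and n = 60 per arm means nobody is lost. Power = Φ[(|p1 − p2| − 1.96 × se0) / se1], where se0 = √[2p̄(1 − p̄)/n] and se1 = √{[p1(1 − p1) + p2(1 − p2)]/n}.

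For 20% against 10%: p̄ = .15, se0 = .0652, se1 = .0645. Then (.10 − 1.96 × .0652) / .0645 = −0.43, and Φ(−0.43) = 33%.

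| Assumed change | 60 per arm | 48 per arm (120 less 20%) |
|---|---|---|
| 10% to 5% | 18% | 15% |
| 20% to 10% | 33% | 28% |
| 30% to 15% | 50% | 42% |
| 50% to 25% | 82% | 72% |
| 60% to 30% | 92% | 85% |
| 50% to 20% | 94% | 88% |

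Power of 80% is reached for common outcomes or large effects, and not for the rarer events.

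**The case against.** Much can be said for the plan, and several stronger readings that a reader might draw do not survive.

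- *That the sample-size chain is wrong.* It is not. For f = .25 with the inferred 4 visits and correlation .5, at the plan's own design effect of 3.0, power is 82% with 72 analysed and 92% with 96.
- *That attempts, deaths and admissions were left out.* The calculation is labelled for Hypotheses 1 and 2, and Hypothesis 1 names suicidality and admissions. They are nominally in scope, and suicidality also includes ideation, so the hypothesis does not rest on rare events alone. The Analysis Strategy allows for binary and count distributions. What is missing is any rate from which power could be judged.
- *That restraint use and disposition need 128 patients.* The figure is for a continuous outcome. These two are mainly categorical, so their requirement depends on rates the documents do not give.
- *That losses of 20% apply to these two outcomes.* The care team supplies those data around the ED stay, so follow-up attrition need not apply. Refused releases could reduce the number, but no rate is given. With all 120 analysed, the continuous benchmark is only 2.5 points short of 80%.
- *That the plan contradicts itself over provider outcomes.* The doubt there is tied to providers lacking time to supply data, and those ratings are to be described only. The conflict exists only if the closing phrase is read literally to include provider ratings.
- *That 120 is promised to deliver power.* The plan says it will strive for 120 for that purpose, which is weaker than a guarantee.

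All of these stand. They narrow the point without removing it: even if the phrase means patient outcomes only, five of the ED primary outcomes have no power basis.

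**Conclusion.** The concern holds in limited form. The calculation supports a power statement for continuous repeated measures under Hypotheses 1 and 2. It does not support one for restraint use, discharge disposition, deaths, attempts or admissions. At the plan's own f, a continuous outcome recorded once falls slightly short at 120. For yes/no outcomes at assumed base rates of 10% to 30%, power to detect a halving is between 18% and 50% with nobody lost. The illustrative figures assume no design effect; any clustering would lower them.

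A reader might go on to infer that 120 is too few or that the event outcomes are certainly underpowered. The documents do not support that, because they state no event rates, and a common outcome or a large effect could be detected with 120. The defect is an unsupported assurance, and it can be corrected in the text. Leaving the visits, correlation and sphericity unstated makes the calculation harder to check, but is not part of the error.

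**What to change.** Amend the last sentence of Statistical Power Considerations in section 5.B:

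1. Delete the closing four words that extend the claim to every outcome, and limit the statement to continuous repeated-measure outcomes under Hypotheses 1 and 2.
2. Add text such as: *Deaths, attempts, admissions, restraint use and discharge disposition carry no power claim. They will be reported as between-arm estimates with 95% confidence intervals, and a non-significant result is not evidence of no effect.*

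The new text should not say that disposition and restraint use are tested as planned. The only parameter the Analysis Strategy names for patient outcomes is the Time by Condition interaction, which these two do not have.

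As a useful addition, state the number of visits, the correlation and the sphericity assumption behind the figure of 24.

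The cost is wording only. The sample size and study procedures do not change, and the Hypothesis 1 tests stay as they are. The downside is a less favourable power statement.

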## C. Monitoring

This study will include a Data and Safety Monitoring Board (DSMB). Relying on [name] (CAMS Treatment Developer) familiarity with the top clinicians and researchers within the field, we selected [name], as the chair of our DSMB. [name] currently serves as a Research Associate Professor at of Clinical Psychology and Psychiatry at the University of Pennsylvania, where his research efforts focus on developing, evaluating, and disseminating interventions for individuals at high risk for suicide. [name] has agreed to serve in the role as our DSMB ED Psychiatrist. [name] has experience in the clinical treatment of suicidal patients and has also focused on training in suicide risk assessment, management, and treatment. Our third DSMB member is [name]. [name] is a board-certified clinical psychologist and current Executive Director of the National Center for Veterans Studies at the University of Utah. [name] has a lengthy history of successful treatment development, research, and treatment of suicide.

The specific goals of this DSMB are:

1. To review procedures for maintaining the confidentiality of data, and quality of data collection, management, and analysis.
2. Provide consultation and procedural recommendations for working with suicidal patients when necessary.
3. Review progress toward meeting enrollment goals.
4. When appropriate, serve as final arbiters of whether a participant should be removed from the protocol.
5. To recommend continuation, discontinuation, modification, or termination of a study based on emerging data (in the study and/or literature) and evaluation of risk/benefit ratio.

Given the nature of this project, we expect the likelihood of items 3 and 4 to be extremely low. However, the formation of the DSMB ensures that we are taking steps to protect the welfare of the study participants. The DSMB will periodically review any modifications to the research design and conduct of the study, and make recommendations according to the NIH policies for data and safety monitoring. An initial meeting of the DSMB and Research Team will be scheduled prior to the start of the research, thereafter members of the DSMB will meet approximately quarterly. If the need arises, the board will schedule additional meetings. At the initial DSMB meeting, the board's criteria for an immediately reportable severe adverse event (SAE) will be established and subsequent reporting will follow this guideline. The study will use the procedures of the NIMH Data Safety Monitoring Board to determine triggers for stopping the study and the DSMB will discuss if additional specific stopping rules should be developed prior to commencing the trial. As per NIMH DSMB procedure, the raw numbers of suicidal events and level of suicidal ideation will be provided in the DSMB reports to allow the DSMB to determine if stopping the study needs to be considered. We will also send recruitment progress updates, participation rates, a detailed summary of all potentially adverse events, as well as a summary of those situations that may not meet the threshold of a potentially adverse event but that nonetheless may be important for the DSMB to consider in advance of their scheduled meetings. In the event that a SAE occurs (e.g., suicide, homicide, physical attack on staff, indication of clinical worsening), the PI will notify the IRB and DSMB within 24 hours of learning of the event. All suicide attempts and emergency department are also reported in the annual IRB and DSMB reports. In trials of acutely suicidal participants, suicide attempts and emergency department are classified as expected events and immediate reporting is required only when clinical worsening is indicated (e.g., a suicide attempt in a patient who has not done so before).

Following each meeting of the DSMB, the DSMB Chair will prepare and send a brief summary report to the PI. The report will document that: (1) a review of recruitment, data, and outcomes has occurred; (2) the number, nature, and outcome of any adverse events occurring during the review period; and (3) reflect the date the review took place. The report will also inform the PIs of the board's conclusion with respect to study progress, any need for modification of the study

protocol or operating procedures, and determination for the study to continue. Upon receipt of the report, the PIs will be responsible for transmitting a copy of the report to the IRB.

[name] will be responsible for managing, storing, and protecting data at the primary study research site. She will work closely with the research staff to maintain continuous, close monitoring and promptly report adverse events to the site PIs, the DSMB, and the IRB. The study coordinators (i.e., EBPI RAs, site PIs, site RAs) will notify [name] of any adverse events within 24 hours of occurring and notification will be forwarded to the DSMB and IRB immediately.

## **D. Storage of Data**

Study data, including qualitative notes from follow up interviews and survey-based data, are stored in a password protected area within a cloud-based encrypted server (Box) that is accessible only to the research team. The data files are coded with the participant's study identification number and time point. The files do not contain identifying information such as the participants' names, but will again contain the participant's study identification number. Survey-based data, including the screening and demographics questionnaire, as well as a brief questionnaire to assess acceptability and clinical relevance, are also stored in SurveyMonkey, where responses are transmitted using a Secure Sockets Layer (SSL) connection and is also encrypted. Like the qualitative notes from the follow up assessments, the Survey Monkey data sources use only the study identification number to identify the participant.

In most cases, participants will complete the surveys directly in SurveyMonkey and/or the data are entered directly by the RA into Survey Monkey. In the rare event that a participant prefers to complete a paper-pencil measure, the data will be immediately entered into SurveyMonkey by a study RA then the paper copy will be destroyed within 24 hours via shredding or secure disposal in a secure shredding bin for later secure disposal. Access to electronic research files is limited to research staff, who are required to log in to Box with a unique user name and password for access.

## **E. Confidentiality of Data**

To protect participants from loss of confidentiality, the following procedures will be employed: Each participant will be assigned a study identification number that does not contain number elements that could be linked back to their identity. Only one document, known as the Master Participant Document (MPD), will link the patient's identity to their study identification number. The MPD file is password protected and stored separate from study data on a cloud-based encrypted server (Dropbox) accessible only to the research team trained in the ethical conduct of human subjects' research. No other data is included in the MPD. Out of an abundance of caution and to ensure HIPAA protections, all electronic files that include patient names or other identifying information (even though not associated with the patient's study ID), will be stored on Dropbox. EBPI has a BAA in place with Dropbox and only assigned researchers (e.g., PI, Research Assistants) will have access to EBPI's Dropbox account.

When applicable (e.g., follow up assessments) study staff will send email and/or text reminders to participants completing survey measures online that includes a link to the online survey questionnaires. Participants will enter their unique study identification number rather than identifying information when completing survey measures (online or via paper/pencil). Data gathered via online surveys will be securely transmitted and stored according to the site's security policy, accessible only to the PIs and research staff via a password-secured account.

Data will be protected and stored as described above in Storage of Data. In addition, we will destroy all files that have any names or other identifying information five years after the study is finished, including the file that links participant names to study IDs.

Information provided to Boys Town counselors, when applicable, will be sent via secure email transfer using Microsoft

365 Message Encryption that is built on the Azure Information Protection platform. Emails will be sent directly to a dedicated Boys Town email address. All identifying information will be destroyed after the call and reports provided by Boys Town counselors to the study PI will be scrubbed of identifying information. Boys Town will use the patients study ID instead of their name or other identifying information, such as initials.

